5.7 Treatment Administration

The randomized treatment assignment will be prepared by the pharmacy. Upon arrival to the operating room, standard vital sign monitors will be placed and the patient will be positioned in the sitting position. After administering light sedation with low-dose midazolam and fentanyl, the skin of the back will be cleaned with chlorhexidine antiseptic. Local anesthesia of the skin, subcutaneous tissue and periosteum of the transverse processes 2.5-cm lateral to each side of the thoracic spine (T2-T8) will be performed using 2–5 ml of lidocaine 10 mg/ml. The paravertebral block injections of study solution will occur using the landmark-based classic or ultrasound-guided technique with a 22-gauge Tuohy needle. Double-blinding of patients (study subjects) and physicians/the study team will be maintained, unless it becomes critically necessary to break double-blinding randomization for medical care. One-half of patients will get subcutaneous injectable normal saline (3 to 5 mL at each of 14 injection sites), and one-half will get 0.5% ropivacaine (up to 0.8 mL/kg, equivalent to 4mg/kg). Immediately after completion of the paravertebral injections or subcutaneous injections, the patients will be repositioned supine and general anesthesia induced in the standard manner. All patients will also receive Fentanyl 1.5 mcg/kg 5-10 minutes prior to surgical incision. The primary anesthesia team in the operating room caring for the patient will not be involved in preparation, randomization, or block placement.

The standard orders for the PCA pump and opioid are per the currently used Sunrise POE order set for plastic surgery patients. No changes will be made to the standard administration of anesthesia or to currently available postoperative orders.

5.8 Justification For Placebo

In clinical trials of surgical interventions, sham procedure is an important scientific control. The sham paravertebral subcutaneous saline injections will contribute to isolate the specific effects of the treatment drug (ropivacaine hcl) as opposed to the patient's perception of having had a regular paravertebral block. Thus, sham paravertebral subcutaneous saline injections serve an analogous purpose to placebo drugs, neutralizing biases such as the placebo effect. Additionally, the subcutaneous paravertebral injections of placebo (normal saline) do not carry increased risks besides the potential risks of the injection process itself. The potential risks associated with the injection process itself include the risk of inadvertent vascular puncture (6.8%), pleural puncture (0.8%) and pneumothorax (0.5%),²⁶ all of which are classified as unlikely events (occurring in 1-10 of every 100 patients). Hence, the administration of placebo will strengthen the study design and any conclusion reached without significantly increasing the risk of complications.

5.9 Dose Modifications

The administration of the blocks will be ceased if the patient is experiencing any unanticipated adverse events (i.e., worse side effects than predicted). (See section 7.1.7 for potential side effects.)

5.10 Supportive Care Guidelines

In general, concomitant medications and therapies deemed necessary for the supportive care and safety of the subject are allowed, provided their use is documented in the medical records and followed up through the Day 7 post-operative visit.

5.11 Duration of Study Participation

Study participation continues through Year 4 post-operatively. However, the majority of data collection will occur during the first 7 days after the participant’s immediate tissue expander reconstruction following mastectomy. An additional study visit will occur in clinic at Day 90 (± 14 days), prior to the participant’s undergoing any additional reconstructive breast surgery procedures. Thereafter, follow-up phone interviews will occur at post-operative Year 2 (± 14 days), and post-operative Year 4 (± 14 days).

Participants are to return to clinic for a Day 90 (± 14 days) follow-up visit. To encourage participation, participant parking and a \$15 gift card will be given (or mailed) to participants who complete the Day 90 visit.

If a participant chooses to withdraw, is withdrawn, or refuses to participate through Day 90, all efforts will be made to collect all Day 90 post-operative data at the time of study withdrawal. Reasons for premature participation/treatment withdrawal will be recorded to the best of the study team’s ability. Reasons for early withdrawal may include the following:

1. Unanticipated or serious adverse events.
2. Inter-current illness that prevents further administration of treatment or would affect assessment of clinical status to a significant degree.
3. Subject becomes pregnant.
4. Subject refuses to continue treatment.
5. Any reason the study physician deems it necessary for the benefit of the participant.
6. Subject is lost to follow-up.

6. Study Calendar

Table 3. Calendar of study events/procedures.

Parameter	Pre-Study	Surgery (Day 0)	Day1	Day 2*	Day 3*	Day 7 (± 2 days)	Day 90 (± 14 days)	Post-Op Years 2 & 4 (± 14 days)
General Patient History Form	X							
Update Medical History		X	X			X	X	X
Treatment administration (Ropivacaine/Placebo)		X						
Intra-Operative Case report Form (CRF)		X						
Adverse Events of Interest/SAE Assessment		X	X	X	X	X	X	
Pain Meds/Opioid Use	X		X	X	X	X	X	
Questionnaires								
Patient Pain Assessment Questionnaire	X		X	X	X	X	X	X

Subjective Pain Survey	X							
BREAST-Q [®] , Pre-Op	X							
BREAST-Q [®] , Post-Op							X	X
RAND-36 Questionnaire	X					X	X	X
Quick DASH Questionnaire	X					X	X	X

Note: Additional tests may be performed at the discretion of the treating investigator as clinically indicated.

* A study team member will call discharged patients on Day 2 and Day 3 to collect data. Phone calls will not occur on weekends but will resume the following Monday. If the patient is not discharged, study follow-up will occur at bedside.

[figure not shown]
7. Pharmaceutical Information

7.1 Ropivacaine (Naropin[®])

7.1.1 Product Identification

Naropin[®] injection contains ropivacaine HCl, which is a member of the amino amide class of local anesthetics. Naropin[®] (ropivacaine HCl) injection is a sterile, isotonic solution that contains the enantiomerically pure drug substance, sodium chloride for isotonicity and water for injection. Sodium hydroxide and/or hydrochloric acid may be used for pH adjustment. It is administered parenterally.

Ropivacaine HCl is chemically described as S-(-)-1-propyl-2',6'-pipercoloxylidide hydrochloride monohydrate. The drug substance is a white crystalline powder, with a molecular formula of $C_{17}H_{26}N_2O \cdot HCl \cdot H_2O$, molecular weight of 328.89 and the following structural formula:

At 25°C ropivacaine HCl has a solubility of 53.8 mg/mL in water, a distribution ratio between n-octanol and phosphate buffer at pH 7.4 of 14:1 and a pKa of 8.07 in 0.1 M KCl solution. The pKa of ropivacaine is approximately the same as bupivacaine (8.1) and is similar to that of mepivacaine (7.7). However, ropivacaine has an intermediate degree of lipid solubility compared to bupivacaine and mepivacaine.

Naropin (ropivacaine hcl) Injection is preservative-free and is available in single dose containers in 2 (0.2%), 5 (0.5%), 7.5 (0.75%) and 10 mg/mL (1%) concentrations. The specific gravity of Naropin (ropivacaine hcl) Injection solutions range from 1.002 to 1.005 at 25°C.

7.1.2 Mode of Action

A) MECHANISM OF ACTION

1) Local anesthetics bind to the internal axoplasmic membrane (presumably a phospholipid receptor) to reduce ion flux, especially the sodium channel, resulting in inhibition of depolarization and subsequent nerve conduction blockade. Ropivacaine may have a greater propensity for blocking small myelinated A fibers and nonmyelinated C fibers (pain fibers) than bupivacaine; sensory blockade with ropivacaine is generally more pronounced than motor blockade, and the intensity and duration of motor block is lower and shorter with ropivacaine than with equal doses of bupivacaine.

a) With single injections of high concentrations of ropivacaine for epidural analgesia, motor blockade was dose-dependent in segments close to the injection site (L2/3); in abdominal muscles, the blockade was partial and not clearly correlated with ropivacaine concentration.

^[1]_{SEP} b) For epidural analgesia, ropivacaine infused continuously at a 0.1% concentration produced motor blockage so slight that all study subjects could be mobilized; at 0.2% and 0.3% concentrations of ropivacaine infusion, blockade was moderate (40% to 50% of baseline force was present).

B) PHARMACOLOGY

1) Ropivacaine is a long-acting amino-amide local anesthetic with pharmacodynamic properties and uses similar to those of bupivacaine. The S(-)-enantiomer of 1-propyl-2,6-pipecoloxylidide, ropivacaine is structurally similar to bupivacaine and mepivacaine. The S(-) and R(+) enantiomers of ropivacaine are equipotent in terms of local anesthetic effects; however, nerve block with the S(-) isomer is slightly longer, and toxicity appears to be less. In contrast to ropivacaine, both bupivacaine and mepivacaine are available as racemic mixtures.

2) Bupivacaine is considered more cardiotoxic than other amide-type local anesthetics, and this is attributed to its R(-) isomer. Ropivacaine was developed to be a less toxic alternative to bupivacaine. In addition to its availability in the S-isomeric form, ropivacaine differs from bupivacaine by substitution of the butyl group by a propyl group; these changes make ropivacaine less lipid soluble and potentially less likely to induce cardiotoxic effects.

3) In vitro and in vivo studies have suggested a similar anesthetic profile with bupivacaine and ropivacaine, but a greater potential for central nervous system toxicity and cardiotoxicity with the former when given in equal doses (milligram-basis);

ropivacaine may have a greater margin of safety between convulsive and lethal doses. Ropivacaine was less likely than bupivacaine to produce mild cardiovascular and central nervous system changes after intravenous infusion in one study involving healthy subjects. The intensity and duration of motor blockade have tended to be less with epidural ropivacaine compared to epidural bupivacaine.

4) Ropivacaine has vasoconstrictor properties. The drug has produced significant blanching and reduced cutaneous blood flow when infiltrated. The addition of epinephrine may not measurably decrease drug absorption or prolong the duration of blockade of ropivacaine.

7.1.3 Storage and Stability

Store solutions at 15-30°C.

Do not freeze. Due to the nature of the Polyamp® and the Polybag® systems, the containers must not be re-autoclaved.

NAROPIN (ropivacaine hydrochloride) solutions are sterile, without preservative and are for single use only. Discard unused portion.

7.1.4 Indications

NAROPIN (ropivacaine hydrochloride) is indicated for:

Analgesia

Acute pain management in connection with:

- Continuous epidural infusion or intermittent bolus administration e.g., postoperative or labour pain;
- Field block e.g. infiltration.

Anaesthesia

Surgical anaesthesia in connection with:

- Epidural block for surgery, including Caesarean section;
- Major nerve block e.g., brachial plexus block;
- Field block e.g., infiltration.

7.1.5 Contraindications

NAROPIN (ropivacaine hydrochloride) is contraindicated:

- In patients with a hypersensitivity to ropivacaine or any other local anaesthetic agent of the amide type;
- For intravenous regional anaesthesia (Bier block);
- In obstetric paracervical block anaesthesia. Use of other local anaesthetics in this technique has resulted in foetal bradycardia and death.

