5.2 Patient Population

All patients presenting to the Johns Hopkins Avon Foundation Breast Center for surgical management of high risk for breast cancer, pre-malignant breast lesions, or breast cancer leading to bilateral mastectomies with reconstruction will be evaluated for participation. Those meeting inclusion criteria and no exclusion criteria may be enrolled into the study.

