5.2.2 Exclusion Criteria

Participants with the following conditions will be ineligible:

- Any concurrent opioid analgesic use (baseline opioid use must be 0 to be eligible).
- Liver dysfunction and/ or cirrhosis.

- Renal insufficiency, with creatinine greater than 1.5 mg/mL.
- Patients weighing less than 50 Kg.
- Concurrent use of the SSRI antidepressant fluvoxamine (Luvox).

Having a tattoo on the back that is too large to permit PVB injections (as determined by the provider performing the procedure).

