5.4 Determination of Eligibility

Potential subjects will be consented by the study investigators or study staff. If determined eligible, subjects will be registered with the study coordinator through the assignment of a study-specific ID number.

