5.5 Randomization

During the study, patients desiring a bilateral mastectomy followed by bilateral immediate tissue expander reconstruction will be randomized to ropivacaine- pre-operatively placed paravertebral blocks or subcutaneous paravertebral saline (placebo) injections at the same site as the paravertebral block. Randomization will be performed by the pharmacy when the medication is requested prior to paravertebral block administration.

A master list of randomization assignments made by the protocol biostatistician will be delivered to the Research Pharmacy at Johns Hopkins. Other key personnel may also receive this list, if required.

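### The amide-anaesthetic hypersensitivity contraindication in 7.1.5 is not carried into the eligibility criteria, so an affected patient can reach randomisation (minor patient-safety correction)

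*Combined protocol and SAP*

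**What the plan says.** Section 7.1.5 lists three contraindications to ropivacaine. The first is use "In patients with a hypersensitivity to ropivacaine or any other local anaesthetic agent of the amide type". The other two concern intravenous regional anaesthesia and obstetric paracervical block, neither of which is used in this trial.

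Section 5.2 gives the enrolment rule: "Those meeting inclusion criteria and no exclusion criteria may be enrolled into the study". The criteria themselves are in 5.2.1 and 5.2.2. Section 5.4 then says: "If determined eligible, subjects will be registered with the study coordinator through the assignment of a study-specific ID number". Section 5.5 sets the moment of allocation: "Randomization will be performed by the pharmacy when the medication is requested prior to paravertebral block administration".

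Section 5.1 requires baseline data, including a general patient history, to be collected before randomisation and surgery. The calendar (section 6, Table 3) shows this as the "General Patient History Form" at the pre-study visit, with a medical history update on the day of surgery. Section 5.11 allows withdrawal for "Any reason the study physician deems it necessary for the benefit of the participant". In 8.3 the investigator undertakes to follow the protocol's instructions.

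**The concern.** A contraindication to the study drug that turns on a patient's own history would normally appear among the exclusion criteria, because those are what staff check at enrolment. Here it appears only in the pharmaceutical section. Under 5.4, investigators or study staff may obtain consent, and a checklist built from 5.2.1 and 5.2.2 would not prompt the question.

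At stake is the safety of a rare patient. If nobody asks, she may be given a drug that the protocol says she must not have. If someone asks only after the pharmacy has allocated treatment, she may have to be withdrawn as a randomised participant. Her enrolment would not breach 5.2, so a check of eligibility against those criteria alone would not flag it.

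**Working it through.** The plan gives no figure on this point, so the check is a comparison of texts.

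**1. Inclusion criteria (5.2.1).** The six items cover sex and age, choice of operation, absence of inflammatory cancer, awareness of the malignancy, understanding of the study, and consent. Items covering hypersensitivity: 0 of 6. The study population entry in the Protocol Summary has none either.

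**2. Exclusion criteria (5.2.2).** The six items are:
- current opioid use
- liver disease
- raised creatinine
- weight below 50 kg
- fluvoxamine use
- a back tattoo too large to allow the injections

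Items covering hypersensitivity: 0 of 6.

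**3. Later steps.** Sections 5.4 (registration), 5.5 (randomisation) and 5.7 (treatment administration) state no allergy check. The only other allergy wording found is an example of a serious event in 9.2.2.

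**4. The two rules applied to one patient.** Take a woman with a known amide reaction who otherwise qualifies.

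| Rule | Outcome |
|---|---|
| 5.2 with 5.2.1 and 5.2.2 | may be enrolled |
| 5.4, 5.5 | may be registered and randomised |
| 7.1.5, binding through 8.3 | must not receive ropivacaine |

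**5. Chance of allocation to ropivacaine.** The planned allocation is 35:35 among 70, so 35/70 = 1/2. In that arm 5.7 gives 0.5% ropivacaine at up to 0.8 mL/kg. At 5 mg/mL (7.1.1) this is 0.8 × 5 = 4 mg/kg, which matches the dose stated in 5.7.

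**6. What stands in the way.** The history required by 5.1 comes before randomisation. Its form is not among Appendices A to F, so its content is unknown, and no rule makes its findings a condition of eligibility. The withdrawal clause in 5.11 is discretionary and applies to someone already participating.

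**7. Number of patients affected.** The documents give no prevalence of amide hypersensitivity, so no expected count can be derived. The nearest statement, in 7.1.7, calls adverse reactions to local anaesthetics very rare unless there is overdose or accidental intravascular injection. It concerns reactions in general, not the frequency of known hypersensitivity.

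**The case against.** The strongest reply is that the protocol already has the rule. Section 7.1.5 is part of it, 8.3 binds the investigator to it, and clinicians are expected to respect a drug's contraindications. A history is a written step before randomisation, and 5.7 leaves standard anaesthetic practice unchanged, so routine questioning would probably catch most cases. The removed consent pages might also mention allergy, though that would not alter the criteria in 5.2.

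Much of this stands. A reader might infer that the protocol permits giving ropivacaine to an allergic patient; it does not. A reader might also infer that nothing precedes randomisation that could reveal the allergy; 5.1 shows otherwise. What remains is narrower: the contraindication is missing from the place where eligibility is decided, and no stated step asks about it before allocation.

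The other exclusions do not prove an oversight. Items such as "Concurrent use of the SSRI antidepressant fluvoxamine (Luvox") do not appear in 7.1.5, so 5.2.2 can be read as adding restrictions to contraindications that apply in their own right. That reading is fair, but it still leaves 5.2 admitting a patient whom 7.1.5 bars from the study drug.

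A further tempting step is to say that placebo patients are exposed too, because 5.7 says that local anaesthesia before the injections "will be performed using 2–5 ml of lidocaine 10 mg/ml", with no distinction by arm. The documents do not state lidocaine's class, so they do not support that claim. The point does not need it.

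**Conclusion.** The point holds as a minor patient-safety correction. Two written rules disagree about the same patient: the eligibility criteria admit her, while the pharmaceutical section bars her from the study drug. She can reach randomisation, with a 1 in 2 chance of being assigned ropivacaine. The likely outcomes are that a clinician catches it in time, or catches it late and withdraws her after randomisation. Exposure is possible but would require both the history and clinical judgement to fail.

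Confidence is high that the criterion is absent from the list. The practical consequence cannot be quantified from the documents. The expectation that cases are very rare is a judgement, consistent with 7.1.7 but not established by it. Sample size, power and analysis are unaffected.

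**What to change.** Add to 5.2.2, and to any eligibility checklist drawn from it: *Known hypersensitivity to ropivacaine or any other amide-type local anaesthetic.* Confirm it at the general patient history required by 5.1, before the pharmacy is asked to randomise. If the history form already asks about drug allergy, it is enough to state that the answer determines eligibility.

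The cost is one line in the exclusion list and at most one screening question, made through the amendment route in 8.1. The effect on accrual should be negligible, and no design figure changes.

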7.1.6 Availability

Absorption: The systemic concentration of local anaesthetics is dependent upon the total dose and the concentration administered, the route of administration, the patient's hemodynamic/circulatory condition, and the vascularity of the injection site. Ropivacaine follows linear pharmacokinetics and the maximum plasma concentration is proportional to the dose.

Ropivacaine shows complete and biphasic absorption from the epidural space. The mean half-lives of the two phases are in the order of 14 min and 4 h. The slow absorption is the rate-limiting factor in the elimination of ropivacaine, which explains why the apparent elimination half-life is longer after epidural than after intravenous administration. Ropivacaine shows dose proportionality at epidural doses up to 250 mg and intravenous doses up to 80 mg.

Distribution: Following intravenous administration, the volume of distribution of NAROPIN is approximately 40 L. NAROPIN is extensively bound to alpha1-acid glycoprotein in plasma with an unbound, i.e. pharmacologically active, fraction of about 6%. An increase in total plasma concentration during continuous epidural infusion has been observed in postoperative patients and is related to the postoperative increase of alpha1-acid glycoprotein. Variations in unbound concentration have been much less than in total plasma concentration.

Ropivacaine readily crosses the placenta and equilibrium, in regard to unbound concentration, is rapidly reached. The degree of plasma protein binding in the foetus is less than in the mother, which results in lower total plasma concentrations in the foetus than in the mother. The ratios of umbilical vein to maternal vein total and free concentrations are 0.31 and 0.74, respectively.

Metabolism: Ropivacaine is extensively metabolized in the liver predominantly to 3- hydroxy-ropivacaine by an aromatic hydroxylation process mediated by cytochrome P4501A2 and N-dealkylation to PPX mediated by CYP3A4. Conjugated and unconjugated 3-hydroxy-ropivacaine represent the major urinary metabolites. Urinary excretion of 4-hydroxy ropivacaine, N-dealkylated pipercoloxylidide (S-PPX) and both the 3-hydroxy and 4-hydroxy N-dealkylated metabolites account for less than 3% of the dose. An additional metabolite, 2- hydroxy-methyl-ropivacaine has been identified, but not quantified in urine. S-PPX and 3- hydroxy ropivacaine are the major metabolites excreted in the urine during epidural infusion. A total S-PPX concentration in the plasma was about half that of total ropivacaine however, mean unbound concentrations of S-PPX were about 7 – 9 times higher than that of unbound ropivacaine following continuous epidural infusion up to 72 hours. The threshold for CNS toxicity in rats due to unbound plasma concentrations of PPX is approximately 12 times higher than that of unbound ropivacaine. S-PPX, 3-hydroxy ropivacaine, and 4-hydroxy ropivacaine have a pharmacological activity in animal models less than that of ropivacaine.

There is no evidence of in vivo racemization of ropivacaine.

Excretion: After intravascular administration, 86% of the total dose of ropivacaine is excreted in the urine of which approximately 1% is the parent compound and 36% is 3- hydroxy-ropivacaine. Ropivacaine has a mean total plasma clearance in the order of 440 mL/min, an unbound plasma clearance of 8 L/min, a renal clearance of 1 mL/min, and a volume of distribution at steady state of 47 L. Ropivacaine has an intermediate hepatic extraction ratio of

about 0.4. The terminal elimination half-life is 1.6 to 1.8 hours after intravenous administration, 4.1-6.5 hours after epidural administration, and 5.7-8.0 hours after brachial plexus block. The total and unbound clearance of epidural ropivacaine at term in pregnancy (223-256 mL/min and 2.8-3.3 L/min, respectively), are lower than that observed in non-pregnant patients.

